ANNEX 3F. POTENTIAL RISK FACTORS CODELISTS for CM					
	between birth and exit date; binary yes/no	Patient/Hospital Registry; D: National Patient Registry			
Offspring Congenital Varicella	ICD-10 diagnosis for the offspring between birth and exit date; binary yes/no	Medical Birth Registry	Literature	1) Gilbert-Barness E. Teratogenic causes of malformations. Ann Clin Lab Sci. 2010 Spring;40(2):99–114. 2) Ferry T, Vial Y, Vaudaux B. [Varicella during pregnancy: consequences for the mother and the newborn]. Rev Med Suisse. 2011 Apr 27;7(292):900–4.	Table 36
Offspring Congenital CMV	ICD-10 diagnosis for the offspring between birth and exit date; binary yes/no	Medical Birth Registry	Literature	Lanzieri TM, Leung J, Caviness AC, Chung W, Flores M, Blum P, et al. Long-term outcomes of children with symptomatic congenital cytomegalovirus disease. J Perinatol. 2017 Jul;37(7):875–80.	Table 32
Offspring Congenital Herpes Simplex Viral Infections	ICD-10 diagnosis for the offspring between birth and exit date; binary yes/no	Medical Birth Registry	Literature	Ferry T, Vial Y, Vaudaux B. [Varicella during pregnancy: consequences for the mother and the newborn]. Rev Med Suisse. 2011 Apr 27;7(292):900–4.	Table 33
Offspring Congenital Toxoplasmosis	ICD-10 diagnosis for the offspring between birth and exit date; binary yes/no	Medical Birth Registry	Literature	Gilbert-Barness E. Teratogenic causes of malformations. Ann Clin Lab Sci. 2010 Spring;40(2):99–114.	Table 35
Offspring Foetal Alcohol Syndrome	ICD-10 diagnosis for the offspring between birth	S: Medical Birth Registry; N: National Patient/Hospital Registry; D:	Literature	1) Mesquita M dos A, Segre CA de M, Mesquita M dos A, Segre CA de M. Congenital malformations in newborns of alcoholic mothers. Einstein (São Paulo). 2010 Dec;8(4):461–6. 2) Grewal J, Carmichael SL, Ma C, Lammer EJ, Shaw GM. Maternal Periconceptional Smoking and Alcohol Consumption and Risk for Select	Table 38

ANNEX 3F. POTENTIAL RISK FACTORS CODELISTS for CM					
	and exit date; binary yes/no	National Patient Registry		Congenital Anomalies. Birth Defects Res A Clin Mol Teratol. 2008 Jul;82(7):519–26.  3)Riley EP, Infante MA, Warren KR. Fetal Alcohol Spectrum Disorders: An Overview. Neuropsychol Rev. 2011 Jun;21(2):73–80.	

ATC: Anatomical Therapeutic Chemical; CMV: Cytomegalovirus; DP: during pregnancy; ICD-10: International Statistical Classification of Diseases and Related Health Problems 10th Revision; LMP2: Last Menstrual Period + 2 weeks; S: Sweden; N: Norway; D: Denmark; NA: Not Applicable; WHO: World Health Organization.

## Annex 3G - Codelists

**Table 8: ASD**

ICD 10	Clinical Code Description
F840	Childhood autism
F841	Atypical autism
F842	Rett's syndrome
F843	Other childhood disintegrative disorder
F845	Asperger syndrome
F848	Other pervasive developmental disorders
F849	Pervasive developmental disorder, unspecified

ICD-10: International Statistical Classification of Diseases and Related Health Problems 10th Revision.

**Table 9: NDD excluding ASD**

ICD 10	Clinical Code Description	Category
F70	Intellectual Disability - Mild	Intellectual disabilities
F71	Intellectual Disability - Moderate	
F72	Intellectual Disability - Severe	
F73	Intellectual Disability - Profound	
F78	Other Intellectual Disability	
F79	Unspecified Intellectual Disability	
F80	Specific developmental disorders of speech and language	Communication disorders
F81	Specific developmental disorders of scholastic skills	Disorders of psychological development
F83	Mixed specific developmental delays	
F84.4	Overactive disorder associated with mental retardation and stereotyped movements	
F88	Other disorders of psychological development	
F89	Unspecified disorder of psychological development	
F99	Mental disorder, not otherwise specified	
R48	Dyslexia and other symbolic dysfunctions, not elsewhere classified	Hyperkinetic disorders
F90	Hyperkinetic disorders	
F988	Other specified behavioural and emotional disorders with onset usually occurring in childhood and adolescence	

ICD 10	Clinical Code Description	Category
F95	Tic disorders	Tic Disorders
F82	Specific developmental disorder of motor function	Movement disorders
F984	Stereotyped movement disorders	
G250	Essential tremor	
G252	Other specified forms of tremor	
G253	Myoclonus	
G255	Other chorea	
G258	Other specified extrapyramidal and movement disorders	
G259	Extrapyramidal and movement disorder, unspecified	
G242	Idiopathic nonfamilial dystonia	
G243	Spasmodic torticollis	
G244	Idiopathic orofacial dystonia	
G245	Blepharospasm	
G248	Other dystonia	
G249	Dystonia, unspecified	
G26	Extrapyramidal and movement disorders in diseases classified elsewhere	

ASD: Autism Spectrum Disorder; ICD-10: International Statistical Classification of Diseases and Related Health Problems 10th Revision; NDD: Neurodevelopmental disorders.

**Table 10: NDD all**

ICD 10	Clinical Code Description	Category
F70	Intellectual Disability - Mild	Intellectual disabilities
F71	Intellectual Disability - Moderate	
F72	Intellectual Disability - Severe	
F73	Intellectual Disability - Profound	
F78	Other Intellectual Disability	
F79	Unspecified Intellectual Disability	
F80	Specific developmental disorders of speech and language	Communication disorders
F81	Specific developmental disorders of scholastic skills	Disorders of psychological development
F83	Mixed specific developmental delays	
F84	Pervasive developmental disorders	
F88	Other disorders of psychological development	
F89	Unspecified disorder of psychological development	
F99	Mental disorder, not otherwise specified	
R48	Dyslexia and other symbolic dysfunctions, not elsewhere classified	
F90	Hyperkinetic disorders	Hyperkinetic disorders
F988	Other specified behavioural and emotional disorders with onset usually occurring in childhood and adolescence	
F95	Tic disorders	Tic Disorders
F82	Specific developmental disorder of motor function	Movement disorders
F984	Stereotyped movement disorders	
G250	Essential tremor	
G252	Other specified forms of tremor	
G253	Myoclonus	
G255	Other chorea	
G258	Other specified extrapyramidal and movement disorders	
G259	Extrapyramidal and movement disorder, unspecified	

ICD 10	Clinical Code Description	Category
G242 G243 G244 G245 G248 G249	Idiopathic nonfamilial dystonia Spasmodic torticollis Idiopathic orofacial dystonia Blepharospasm Other dystonia Dystonia, unspecified	
G26	Extrapyramidal and movement disorders in diseases classified elsewhere	

ICD-10: International Statistical Classification of Diseases and Related Health Problems 10th Revision; NDD: Neurodevelopmental disorders.

**Table 11: CM all**

Subgroups	ICD 10 - major	MAJOR-specific exclusions	ICD 10 - minor	MINOR-specific exclusions
Nervous System	Q00 Q01 Q02 Q03 Q04 Q05 Q06 Q07			-
Eye	Q10 Q11 Q12 Q13 Q14 Q15		Q101 Q102 Q103 Q105 Q135 Q752	
Ear, face, and neck	Q16 Q17 Q18		Q170 Q171 Q172 Q173 Q174 Q175 Q179 Q180 Q181 Q182 Q184 Q185 Q186 Q187 Q189	
Congenital Heart Defects	Q20 Q21 Q22 Q23 Q24 Q25 Q26	Q250 if: -non-live birth  -live birth with gestational age is <37 weeks  Q270"	Q270 Q250	Q250 if: -non-live birth  -live birth with gestational age is >37 weeks
Respiratory	Q30 Q31 Q32 Q33 Q34		Q315 Q320 Q331 Q309	

Subgroups	ICD 10 - major	MAJOR-specific exclusions	ICD 10 - minor	MINOR-specific exclusions
Oro-facial	Q35 Q36 Q37	If codes Q35-Q37 co-occur with codes Q00 or Q041 or Q042 classify record under 'Nervous System' subgroup		
Digestive system	Q38 Q39 Q40 Q41 Q42 Q43 Q44 Q45 Q790		Q381 Q382 Q400 Q401 Q430	
Abdominal wall defects	Q792 Q793 Q795			
Urinary	Q60 Q61 Q62 Q63 Q64		Q610 Q627 Q633	
Genital	Q50 Q51 Q52 Q54 Q55 Q56		Q523 Q525 Q540	

Subgroups	ICD 10 - major	MAJOR-specific exclusions	ICD 10 - minor	MINOR-specific exclusions
Limb	Q65 Q66 Q69 Q70 Q71 Q72 Q73 Q74		Q653 Q654 Q655 Q656 Q662 Q663 Q664 Q665 Q666 Q667 Q668 Q669 Q845	
Chromosomal	Q90 Q91 Q92 Q93 Q96 Q97 Q98 Q99	Q936	Q950 Q951	
Musculo-skeletal	Q67 Q68 Q77 Q782 Q783 Q784 Q785 Q786 Q787 Q788		Q680 Q672 Q673 Q753 Q670 Q671 Q674 Q677 Q676 Q678 Q675 Q683 Q684 Q685 Q760 Q765	
Craniosynostosis	Q750			
Situs inversus	Q893			
Conjoined twins	Q894			
Congenital skin disorders	Q80 Q81 Q82		Q825 Q833	

Subgroups	ICD 10 - major	MAJOR-specific exclusions	ICD 10 - minor	MINOR-specific exclusions
Genetic syndromes + microdeletions	Q751 Q754 Q87 Q936 D821			
Genetic syndromes + sequences	Q606 Q794			

ICD-10: International Statistical Classification of Diseases and Related Health Problems 10th Revision.  
 List excludes teratogenic syndromes, foetal alcohol syndrome and maternal infections causing malformations.

**Table 12: CM major**

Subgroups	ICD 10 -major	ICD 10 -minor (EXCLUDE)	Other exclusions
Nervous System	Q00 Q01 Q02 Q03 Q04 Q05 Q06 Q07		
Eye	Q10 Q11 Q12 Q13 Q14 Q15	Q101 Q102 Q103 Q105 Q135 Q752	
Ear, face, and neck	Q16 Q17 Q18	Q170 Q171 Q172 Q173 Q174 Q175 Q179 Q180 Q181 Q182 Q184 Q185 Q186 Q187 Q189	

Subgroups	ICD 10 -major	ICD 10 -minor (EXCLUDE)	Other exclusions
Congenital Heart Defects	Q20 Q21 Q22 Q23 Q24 Q25 Q26	Q250 if:  -non-live birth  -live birth with gestational age is <37 weeks  Q270	
Respiratory	Q30 Q31 Q32 Q33 Q34	Q315 Q320 Q331 Q309	
Oro-facial	Q35 Q36 Q37		If codes Q35-Q37 co-occur with codes Q00 or Q041 or Q042 classify record under 'Nervous System' subgroup
Digestive system	Q38 Q39 Q40 Q41 Q42 Q43 Q44 Q45 Q790	Q381 Q382 Q400 Q401 Q430	
Abdominal wall defects	Q792 Q793 Q795		
Urinary	Q60 Q61 Q62 Q63 Q64	Q610 Q627 Q633	
Genital	Q50 Q51 Q52 Q54 Q55 Q56	Q523 Q525 Q540	

Subgroups	ICD 10 -major	ICD 10 -minor (EXCLUDE)	Other exclusions
Limb	Q65 Q66 Q69 Q70 Q71 Q72 Q73 Q74	Q653 Q654 Q655 Q656 Q662 Q663 Q664 Q665 Q666 Q667 Q668 Q669 Q845	
Chromosomal	Q90 Q91 Q92 Q93 Q96 Q97 Q98 Q99	Q950 Q951	Q936
Musculo-skeletal	Q67 Q68 Q77 Q782 Q783 Q784 Q785 Q786 Q787 Q788	Q680 Q672 Q673 Q753 Q677 Q676 Q678 Q675 Q683 Q684 Q685 Q760 Q765 Q670 Q671 Q674	
Craniosynostosis	Q750		
Situs inversus	Q893		
Conjoined twins	Q894		
Congenital skin disorders	Q80 Q81 Q82	Q825 Q833	

Subgroups	ICD 10 -major	ICD 10 -minor (EXCLUDE)	Other exclusions
Genetic syndromes + microdeletions	Q751 Q754 Q87 Q936 D821		
Genetic syndromes + sequences	Q606 Q794		

ICD-10: International Statistical Classification of Diseases and Related Health Problems 10th Revision.

List excludes teratogenic syndromes, foetal alcohol syndrome and maternal infections causing malformations.

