#### **Secondary outcome**

CM will be evaluated as a composite endpoint among live births within 12 years after birth for Denmark and within 10 years after birth for Norway, spontaneous abortions (during the second or third trimester, Norway and Denmark only) and stillbirths (during the second or third trimester, Norway and Denmark only) as a diagnosis of at least one of the following ICD-10 codes defined as CM according to the EUROCAT categories Guide 14. CM will be defined as a diagnosis of at least one of the ICD-10 codes presented in codelist Table 11. Please note that major CM codelist is presented separately in Table 12 and minor CM codelist in Table 13.

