#### 9.3.2.2 Congenital malformations

With the objective of investigating the risk of CM in offspring paternally exposed to valproate, all CM will be included in the comparative analysis, with the caveat that minor CM are usually under reported, therefore estimates could be under-estimated (17). However, a sensitivity analysis will be performed to address this concern (see section 9.7.5, *Broader definition of CM for secondary outcome*), for Norway and Denmark only.

The **index date (start of follow-up)** will be defined as the start of the 2nd trimester or 3rd trimester (12th or 22nd week of gestation), respectively for Norway and Denmark, and from offspring birth date for Sweden from which pregnancies will be followed up for the outcome of interest.

The **exit date/end of follow-up** will be defined as the end of the study period (31 December 2018 for Denmark and 31 December 2019 for Sweden and Norway), death, emigration (where available), reaching the age of 12 years for Denmark and the age of 10 years for Norway) or date of first diagnosis of the outcome at study, which-ever is the soonest.

The analysis of the secondary outcome of CM will be defined according to the presence of at least one of the following criteria:

- an ICD-10 code of CM among live births
- an ICD-10 code of CM in diagnosis/reason for spontaneous abortion/stillbirth (Norway and Denmark only)

The analysis will focus on all CMs, with further substratification by body system organ class. The ICD-10 codes for all CMs are presented in codelist Table 11.

---

 Period between LMP2 (date of conception) and date of birth is immortal - child must survive to be eligible and diagnosis of ASD cannot occur *in utero*

 CM will be classified according to the EUROCAT categories Guide 14 (section 3.3 in EUROCAT Subgroups of congenital anomalies (18)).

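### Table 11 does not deliver the all-CM endpoint: within Q76 only two minor codes count, Q53, Q28 and Q85 are absent, and no stated exclusion explains the gaps

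*Protocol*

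**What the plan says.** Section 9.3.2.2 states that "all CM will be included in the comparative analysis", with a caveat about under-recording of minor CM, so major and minor are both meant. It then says: "The ICD-10 codes for all CMs are presented in codelist Table 11". The abstract (section 4, Secondary outcome) describes the codes as those "defined as CM according to the EUROCAT categories Guide 14" and makes a case depend on at least one code in Table 11.

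In Annex 3G:

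- **Musculo-skeletal, major** (same in Tables 11 and 12): "Q67 Q68 Q77 Q782 Q783 Q784 Q785 Q786 Q787 Q788".
- **Musculo-skeletal, minor** (Table 11) ends: "Q675 Q683 Q684 Q685 Q760 Q765". Table 12 repeats these codes in its exclude column: "Q677 Q676 Q678 Q675 Q683 Q684 Q685 Q760 Q765 Q670 Q671 Q674".
- **Genital** (Table 11): major "Q50 Q51 Q52 Q54 Q55 Q56", minor "Q523 Q525 Q540".
- **Footnote to Tables 11, 12 and 13**: three groups are left out, namely syndromes caused by teratogens, foetal alcohol syndrome, and malformations due to maternal infection.

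**The concern.** A code missing from Table 11 makes its bearer a non-case, whatever the endpoint is called. Within Q76 the rule runs backwards: the two codes that the protocol itself labels minor make a child a case, and the rest of the category does not. The genital row steps from Q52 to Q54, so Q53 counts nowhere.

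Two outputs are affected. The first is the composite secondary endpoint. The second is the description by organ class under exploratory objective 8, which section 9.7.4 justifies by the lack of any expected pattern of CM after paternal exposure. If no pattern is expected, blocks dropped without comment are blocks where nothing can be seen, and the musculo-skeletal and genital rows do not cover what their names say.

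**Working it through.** There is no stated figure to reproduce. The check sets the code lists against the promise in section 9.3.2.2.

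**Step 1: coverage of Q00 to Q99.** Every major and minor code of Table 11 was compared with the 100 three-character positions.

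- Listed in full as a three-character major code: 74.
- Listed only through selected four-character codes: 9.
- Not listed at all: 17.
- Check: 74 + 9 + 17 = 100.

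**Step 2: the nine partly listed categories.**

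| Category | Codes that count | Class in Table 11 |
|---|---|---|
| Q27 | Q270 | minor |
| Q75 | Q750 to Q754 | major and minor |
| Q76 | Q760, Q765 | minor |
| Q78 | Q782 to Q788 | major |
| Q79 | Q790, Q792 to Q795 | major |
| Q83 | Q833 | minor |
| Q84 | Q845 | minor |
| Q89 | Q893, Q894 | major |
| Q95 | Q950, Q951 | minor |

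Of the ten positions Q760 to Q769, two count. The other eight (Q761 to Q764 and Q766 to Q769) appear in neither column. Q27, Q83, Q84 and Q95 show the same pattern of minor codes only. Q780, Q781, Q789, Q791 and all of Q89 except Q893 and Q894 are unlisted.

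**Step 3: the 17 absent positions.** Thirteen (Q08, Q09, Q19, Q29, Q46 to Q49, Q57 to Q59, Q88, Q94) are not held against the list, because the protocol does not show that they are codes in use. Q86 may be explained by the footnote. That leaves 17 − 13 − 1 = 3: Q28, Q53 and Q85. Of these, Q85 is demonstrably in use, since Table 51 takes Q851 as an offspring diagnosis.

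**Step 4: declared exclusions.** None of the three groups in the footnote is a reason to drop the rest of Q76, or Q53, Q28, Q85 or the Q78 codes.

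**Step 5: could this be a reading error?** Tables 11 and 12 carry the same major rows, and Table 13 repeats the minor ones. Loss of a code when the PDF was read is unlikely.

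**Step 6: size.** The protocol gives no frequency for any single code, so the number of events lost cannot be computed.

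**The case against.** *All means major plus minor, not the whole of ICD-10 chapter Q.* That is a fair reading of section 9.3.2.2, and Tables 12 and 13 support it. It does not rescue the list: no rule of major plus minor makes Q760 and Q765 cases and the other Q76 codes non-cases.

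*The outcome follows EUROCAT, which is a selected classification.* This stands in part. The guide is not at hand, so it cannot be said that any given omission is a mistake. But the protocol does not attribute the omissions to the guide, and a footnote that declares three exclusions leads the reader to expect no others.

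*These are the working lists shown to the regulator, and results have been reported.* The amendment log and the milestones say so. That is a reason to show old and new results together, not to leave the definition unexplained.

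A reader might also infer from the exclude column of Table 12 that Q76 was meant to be in the major list and was dropped by accident. The column does not show this. It repeats the minor list, and seven other minor codes (Q270, Q752, Q753, Q833, Q845, Q950, Q951) also have no parent in the major list.

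Nor does the protocol print titles for Q76, Q760, Q765 or Q53. Calling the counted codes trivial and the uncounted ones serious would rest on outside knowledge, and the point needs only the codes and the protocol's own minor label.

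**Conclusion.** The point holds as a definitional fault in a secondary endpoint and in objective 8. Table 11 is not all CM: eight of ten Q76 positions do not count, four further categories enter only through minor codes, three are wholly absent, and parts of Q78, Q79 and Q89 are unlisted, all without a stated reason. Children with only such codes are counted as non-cases. This rests on Table 11 being applied as printed.

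Three stronger conclusions are tempting and are not supported:

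- **A percentage of cases lost.** One could assume a frequency for Q53 and divide by the 3% or 37.1 per 1000 in section 9.5. The frequency has no source in the protocol. The denominator is also wrong: it refers to major CM, and the 37.1 per 1000 counts live births only up to 1 year of age, while the endpoint is major plus minor CM followed to 12 years (10 in Norway).
- **A loss of the stated power.** The total of 826 comes from an assumed 3% risk and an effect size of 2.5 for major CM, not from the code list. Section 9.5 projects about 1720 offspring for Norway and 1580 for Denmark.
- **A biased odds ratio.** The same list applies to both exposure groups, and nothing in the protocol gives a direction.

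**What to change.** Check Tables 11 to 13 code by code against the EUROCAT guide that the protocol cites. Add every code that has no stated reason for omission, at least the rest of Q76 and Q53, in the major or minor class which that guide gives. The class should not be chosen by judgement here. The check must cover Q27, Q28, Q78, Q79, Q83, Q84, Q85, Q89 and Q95 as well, or the amended list will still fall short of its name. Then re-derive Table 11 as the union of the major and minor lists.

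Name each intended omission in the footnote. If any remain, stop calling the endpoint all CM.

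The cost is a code-list edit and a re-run of the CM analyses. For a fixed cohort, added codes can only leave the case count unchanged or raise it, so results should be shown once under both lists to keep them comparable with what has been reported.

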**Table 13: CM minor**

Subgroups	ICD 10	Exclusions
Eye	Q101 Q102 Q103 Q105 Q135 Q752	
Ear, face, and neck	Q170 Q171 Q172 Q173 Q174 Q175 Q179 Q180 Q181 Q182 Q184 Q185 Q186 Q187 Q189	
Congenital Heart Defects	Q250 if: -non-live birth -live birth with gestational age is <37 weeks Q270	Q250 if: -non-live birth -live birth with gestational age is >37 weeks
Respiratory	Q315 Q320 Q331 Q309	
Digestive system	Q381 Q382 Q400 Q401 Q430	
Urinary	Q610 Q627 Q633	
Genital	Q523 Q525 Q540	

Subgroups	ICD 10	Exclusions
Limb	Q653 Q654 Q655 Q656 Q662 Q663 Q664 Q665 Q666 Q667 Q668 Q669 Q845	
Chromosomal	Q950 Q951	
Musculo-skeletal	Q680 Q672 Q673 Q753 Q677 Q676 Q678 Q675 Q683 Q684 Q685 Q760 Q765 Q670 Q671 Q674	
Congenital skin disorders	Q825 Q833	

ICD-10: International Statistical Classification of Diseases and Related Health Problems 10th Revision.  
 List excludes teratogenic syndromes, foetal alcohol syndrome and maternal infections causing malformations.

**Table 14: Study drugs**

ATC code	Name (5th level ATC, chemical substance)	4th level ATC, chemical subgroup
N03AG01	Valproate (valproic acid)	Fatty Acid derivatives
N03AG02	Valproate (valpromide)	Fatty Acid derivatives
N03AX09	Lamotrigine	Other Antiepileptics
N03AX14	Levetiracetam	Other Antiepileptics

ATC: Anatomical Therapeutic Chemical.

**Table 15: Lamotrigine**

ATC code	Name (5th level ATC, chemical substance)	4th level ATC, chemical subgroup
N03AX09	Lamotrigine	Other Antiepileptics

ATC: Anatomical Therapeutic Chemical.

**Table 16: Levetiracetam**

ATC code	Name (5th level ATC, chemical substance)	4th level ATC, chemical subgroup
N03AX14	Levetiracetam	Other Antiepileptics

ATC: Anatomical Therapeutic Chemical.

**Table 17: Valproate**

ATC code	Name (5th level ATC, chemical substance)	4th level ATC, chemical subgroup
N03AG01	Valproate (valproic acid)	Fatty Acid derivatives
N03AG02	Valproate (valpromide)	Fatty Acid derivatives

ATC: Anatomical Therapeutic Chemical.

**Table 18: Bipolar**

ICD 10	Clinical Code Description
F25	Schizoaffective disorder
F31	Bipolar Affective Disorder

ICD 10: International Statistical Classification of Diseases and Related Health Problems 10th Revision.

**Table 19: Epilepsy**

ICD 10	Clinical Code Description
G40	Epilepsy and recurrent seizures

ICD-10: International Statistical Classification of Diseases and Related Health Problems 10th Revision.

**Table 20: Mania**

ICD 10	Clinical Code Description
F30	Manic episode

ICD-10: International Statistical Classification of Diseases and Related Health Problems 10th Revision.

**Table 21: Intrauterine Growth Restriction- IGR**

ICD 10	Clinical Code Description
O36.5	Maternal care for poor foetal growth
P05.0	Light for gestational age
P05.1	Small for gestational age
P05.9	Slow foetal growth, unspecified
P07.0	Extremely low birth weight
P07.1	Other low birth weight

ICD-10: International Statistical Classification of Diseases and Related Health Problems 10th Revision.

**Table 22: Perinatal mortality**

ICD 10	Clinical Code Description
P95	Still birth
Z371	Single Stillbirth
Z37.3	Twins, one liveborn and one stillborn
Z37.4	Twins, both stillborn
Z37.7	Other multiple births, all stillborn
Z37.6	Other multiple births, some liveborn

ICD-10: International Statistical Classification of Diseases and Related Health Problems 10th Revision.

**Table 23: Live birth**

ICD 10	Clinical Code Description
Z37.0	Single live birth
Z37.2	Twins, both liveborn
Z37.5	Other multiple births, all liveborn
Z38	Liveborn infants according to place of birth

ICD-10: International Statistical Classification of Diseases and Related Health Problems 10th Revision.

**Table 24: Non-live birth**

ICD 10	Clinical Code Description
P95	Still birth
Z371	Single Stillbirth
Z37.3	Twins, one liveborn and one stillborn
Z37.4	Twins, both stillborn
Z37.7	Other multiple births, all stillborn
O312	Continuing pregnancy after intrauterine death one foetus or more
O36.4	Maternal care for intrauterine death
O021	Missed Abortion
O03	Spontaneous Abortion
O311	Continuing pregnancy after abortion of one foetus or more
Z37.6	Other multiple births, some liveborn

ICD-10: International Statistical Classification of Diseases and Related Health Problems 10th Revision.

